10.3 POPULATIONS FOR ANALYSES

The primary analysis population will be the modified intention-to-treat (MITT) population. All randomized subjects who complete at least one dose of the study drug will be included in the analysis. Because some patients may withdraw or have a change in clinical status precluding dosing of study drug (eg. post-randomization lactic acidosis), we may randomize additional patients to achieve the enrollment goal of 32 patients who are randomized and treated with at least one dose of the study drug. We expect this to be an uncommon occurrence. Patients who are randomized but do not undergo any study procedures or receive at least one dose of the study product do not contribute any data and will not be included in the study analysis.

10.4 STATISTICAL ANALYSES

10.4.1 GENERAL APPROACH

We will use the Mann-Whitney U or t-test, chi-square (χ^2) or Fisher's exact tests to analyze baseline demographics and clinical characteristics between the treatment groups. Distribution of numerical outcomes will be evaluated prior to any analysis. All statistical analyses will be performed using SAS v 9.4 or newer versions (Cary, NC) or equivalent statistical packages. The detailed statistical analysis of this study can be found in the Statistical Analysis Plan.

10.4.1 ANALYSIS OF THE PRIMARY SAFETY ENDPOINT

The primary analysis population for the primary safety endpoint will be the MITT population. All randomized subjects treated with at least one dose of the study drug will be included in the analysis.

We will examine AEs by the type of event, as well as by body system class, and we will compare the occurrence of specific AEs in each group, as well as the number of AEs per patient in each group.

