1.4 DEFINITIONS

Acute Kidney Injury: Acute kidney injury network Stage 3 disease, defined as a threefold increase in creatinine from baseline or the need for dialysis

Completing 48 hours of UAB (from weaning form): Defined as the date (calendar day) that the subject reaches exactly 48 hours of UAB. Example: if subject meets UAB at 1900 on 6/1/06 and does not return to AB, then the date of completing 48 hours of UAB would be 6/3/06.

Date of first UAB (from Study Termination form): Defined as the first day that the subject is on UAB from midnight to midnight. Example: if subject meets UAB at 1900 on 6/1/06, then the date of first UAB would be 6/2/06, as long as subject does not return to AB on 6/2/06.

Day zero: Defined as day of randomization. Study days are calendar days.

Drug held/hold drug: Study medication withheld for 24 hours.

Drug permanently discontinued: Study medication stopped for remainder of the trial.

Enrollment: The primary analysis population will be the modified intention-to-treat (MITT) population. All randomized subjects treated with at least one dose of the study drug will be included in the analysis. Because some patients may withdraw or have a change in clinical status precluding dosing of study drug (eg. post-randomization lactic acidosis), we may randomize additional patients to achieve the enrollment goal of 32 patients who are randomized and treated with at least one dose of the study drug. We expect this to be an uncommon occurrence. Patients who are randomized but do not undergo any study procedures or study treatment will not be included in the study analysis.

Extubation: Removal of an orotracheal, nasotracheal tube, or unassisted breathing with a tracheostomy.

Home: level of residence or health care facility where the patient was residing prior to hospital admission

Hospital Mortality to Day 60: This primary endpoint includes all deaths following randomization in any health care facility prior to discharge “home” until study day 60. Study subjects still in a health care facility at study day 61 are considered alive for this endpoint.

Interruption of Dosing During Drug Administration: Study medication prematurely stopped prior to 90 minutes.

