9.7.4 TIME PERIOD AND FREQUENCY FOR EVENT ASSESSMENT AND FOLLOW-UP

Designated blinded study physicians will determine daily if any clinical adverse events occur during the period from enrollment to study day 7. Adverse event collection begins after the patient or surrogate has signed informed consent and has received study drug or undergone study procedures. If a patient experiences an adverse event after consent, but prior to receiving study product, the event will NOT be collected unless the investigator feels the event may have been caused by a protocol procedure. The designated blinded study physician will evaluate any changes in laboratory values and physical signs and will determine if these changes are clinically important. All clinically important adverse events will be recorded in the case report form regardless of attribution to study product. After study day 7, adverse events are not required to be reported unless the investigator feels the events were related to either study product or a protocol procedure.

All AEs including local and systemic reactions not meeting the criteria for SAEs will be captured on the appropriate case report form (CRF). Information to be collected includes event description, time of onset, clinician's assessment of severity, relationship to study product (assessed only by those with the training and authority to make a diagnosis), and time of resolution/stabilization of the event. All AEs occurring while on study must be documented appropriately regardless of relationship. All AEs will be followed to adequate resolution. Any medical condition that is present at the time that the participant is screened will be considered as baseline and not reported as an AE. However, if the pre-existing medical condition deteriorates at any time between the first study product administration and study day 7, it will be recorded as an AE. Organ failures related to ARDS or the patient's underlying condition that are systematically captured by the protocol should not be reported as adverse events ***unless they are considered to be study related.***

Changes in the severity of an AE will be documented to allow an assessment of the duration of the event at each level of severity to be performed.

AEs will be followed for outcome information until resolution or stabilization or until 28 days (or hospital discharge whichever occurs first) after enrollment.

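### The comparison of AEs per patient has no time-at-risk denominator, so it can understate the AE rate in an arm with more early deaths

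*Combined protocol and SAP*

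**What the plan says.** The primary safety analysis is made in the modified intention-to-treat population: "All randomized subjects treated with at least one dose of the study drug will be included in the analysis". In that population the plan will compare how often specific AEs occur in each arm, "as well as the number of AEs per patient in each group". The section mentions no patient-days, no rate, and no rule for patients who die or withdraw before day 7.

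The collection window is set elsewhere. Section 9.7.4 says: "Designated blinded study physicians will determine daily if any clinical adverse events occur during the period from enrollment to study day 7". It also says: "Adverse event collection begins after the patient or surrogate has signed informed consent and has received study drug or undergone study procedures". Events before the first dose are in effect excluded: "If a patient experiences an adverse event after consent, but prior to receiving study product, the event will NOT be collected", unless the investigator attributes them to a protocol procedure. Section 1.4 fixes the clock: "Day zero: Defined as day of randomization". The window therefore opens at about the first dose. It closes on a day counted from randomization, or earlier if the patient dies.

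The protocol expects some early deaths. Section 4.4 ends the mtDNA comparison at day 5 or at death, and section 7.1.9 lists death as one way in which the three-day treatment ends.

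**The concern.** AEs through day 7 belong to the primary safety endpoint (section 4.3). A raw count per patient is the daily AE rate multiplied by the days observed. If more patients in one arm die in the first days, that arm has fewer days in which AEs can be recorded, and its mean count falls even when its daily rate equals that of the other arm. The reverse also holds: if iCO reduced early deaths, its patients would be observed for longer and could show more AEs. In both cases the comparison partly reflects survival. Sections 9.7.2 and 9.7.4 add to this by keeping ARDS-related organ failures out of AE reporting unless they are judged study related, so an early death from organ failure may add nothing to the count.

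**Working it through.** The plan gives no expected count per patient, so there is no figure of its own to reproduce on this point. The nearest safety figure is Table 6 in section 10.2, the chance of at least one AE, 1 − (1 − p)^n. At p = 0.10, n = 14 gives 0.77, as printed, and the labelled n = 16 gives 0.81. All seven rows match n = 14, which is 16 less the 10% loss (14.4). Nothing below depends on that label.

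**Inputs from the protocol.** 16 patients per arm (section 10.2). A window of about 7 days: the first dose is due within 24 hours of randomization (section 6.3), and collection ends at study day 7 (sections 1.4 and 9.7.4).

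**Assumptions.** The share dead by day 7 (q) and the AEs expected over a full window (m) are not in the documents. The daily AE rate is taken as constant and the same in both arms, and as no higher in patients who die. Deaths are spread evenly over the window unless stated.

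**Step 1, count ratio at equal daily rates.** Mean days at risk = 7 × (1 − q/2). The ratio is the arm with more deaths over the other arm.

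- 20% v 10% dead: 0.90 / 0.95 = 0.95
- 30% v 10%: 0.85 / 0.95 = 0.895
- 40% v 10%: 0.80 / 0.95 = 0.84
- 30% v 10%, all deaths on day 1: (7 − 0.3 × 6) / (7 − 0.1 × 6) = 5.2 / 6.4 = 0.81

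At 30% v 10%, a daily rate truly 12% higher (1 / 0.895 = 1.12) would show equal counts. Events per patient-day return 1.00 in every row.

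In numbers of patients, k excess deaths on day d give 1 − k(7 − d) / (16 × 7). Two on day 3 give 0.93, three on day 2 give 1 − 15/112 = 0.87, and four on day 2 give 0.82.

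**Step 2, each death also counted as one AE (30% v 10%).** Ratio = (0.85m + 0.30) / (0.95m + 0.10).

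- m = 0.5: 0.725 / 0.575 = 1.26
- m = 1: 1.15 / 1.05 = 1.10
- m = 2: 2.00 / 2.00 = 1.00
- m = 4: 3.70 / 3.90 = 0.95

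**Step 3, how often the direction misleads.** In a Poisson simulation (16 per arm, 40,000 runs, 30% v 10% dead, equal rates, m = 2), the arm with more deaths had the lower mean count in 63% of trials. With patient-day rates it was 50%. With deaths counted as AEs, the lower mean count occurred in 47%.

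**Step 4, late first doses.** A first dose one day late costs 1 of 7 days. If an extra 25% of one arm start a day late, the ratio is 1 − 0.25/7 = 0.96.

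**Step 5, incidence of a specific AE.** For a seven-day risk of 20% at constant hazard, H = −ln(0.8) = 0.223. A patient dying at a uniformly distributed time has an average risk of 1 − 0.2/0.223 = 0.104. Observed incidence is 0.9 × 0.20 + 0.1 × 0.104 = 19.0% at 10% dead and 0.7 × 0.20 + 0.3 × 0.104 = 17.1% at 30% dead. The gap of 1.9 points is about 0.3 of a patient in 16.

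**The case against.** The strongest reply is that this is one descriptive item among several. The primary safety endpoint rests on COHb levels and the incidence of AEs. Section 9.7.5 tabulates participants, counting each once per category, and plans no formal test between groups. An excess of early deaths large enough to matter here would itself be the safety finding. In-hospital deaths go to the DSMB within 7 days of the DCC being notified (section 9.7.6), and mortality is compared by arm in a Cox model (section 10.4.3). The shift is also small beside the noise: with 2.1 AEs per patient there are 33.6 events per arm, and a Poisson 95% interval around a ratio of 1 is exp(±1.96 × √(2/33.6)), or 0.62 to 1.61.

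Most of this stands, and it limits the weight of the point. It does not supply the missing denominator. The Cox analysis reports survival at 28, 60 and 180 days, and no display sets deaths through day 7 beside the AEs. A descriptive comparison over unequal observation times can still be misread.

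A reader might go further and infer that the arm with more early deaths or later first doses will show fewer AEs and look safer. The documents do not support that. Dying patients may have more AEs per day. A fatal MI or stroke within 48 hours of a dose is already a listed event. The organ-failure exclusion does not apply to events judged study related. Death is a seriousness criterion in section 9.7.2, but whether each death is an AE is not stated. Late dosing is a weak route: a delay before any dose cannot be a drug effect, so under 1:1 randomization an imbalance would be mainly chance.

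**Conclusion.** The point holds in a limited form. One component of the primary safety analysis compares raw AE counts over windows that early death can shorten, so it can understate the AE rate in the arm with more early deaths. At equal daily rates the shift is about 5% to 19% across the assumed mortality differences. It can disappear or reverse if deaths are counted as AEs. These sizes rest on assumed mortality, a constant AE rate, and dying patients having no more AEs than others.

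It would be too strong to conclude that the primary safety analysis as a whole is biased, or that an excess of early deaths would be hidden, because incidence and deaths are examined separately. The separate Statistical Analysis Plan to which section 10.4.1 (General Approach) refers for detail is not part of the text reviewed, so an exposure adjustment there cannot be ruled out. This is an inexpensive improvement to the safety table.

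**What to change.** In section 10.4.1 (Analysis of the Primary Safety Endpoint), keep the count per patient and add the following:

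- AEs per patient-day at risk, from first dose to the earliest of death, withdrawal or the end of day 7, by arm, with a rate ratio and confidence interval.
- Administration-related events also per dose given. Most are tied to 6-hour or 48-hour windows after a dose, so patient-days to day 7 do not measure the opportunity for them. Section 10.4.3 allows analysis by number of doses only for secondary and exploratory endpoints.
- Deaths through day 7 by arm in the same table.
- A statement of whether a death counts as an AE.

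The rate ratio and interval are estimates, so they fit the statement in section 9.7.5 that no formal testing is planned. The word compare in section 10.4.1 should be reconciled with that statement. A regression model is not needed at 16 per arm.

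No new data are required: treatment times (section 7.4), AE onset (section 9.7.4) and duration of survival (section 8.3) are already collected. The cost is a few lines of text and a slightly longer safety table. The rate assumes a roughly constant hazard over 7 days and will be imprecise at 16 per arm.

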10.4.2 ANALYSIS OF THE PRIMARY EFFICACY ENDPOINT

We will use the Mann-Whitney U test to compare changes in mtDNA (copies/ μ l) from baseline to day 5 (or death whichever comes first) between treatment arms. Log transformed mtDNA will be analyzed using repeated measures analysis of covariance (ANCOVA) to assess the effects of treatment, time, and the interaction between time and treatment, while incorporating between-patient variation in baseline measurements and important covariates including age and severity of ARDS (SAS PROC MIXED). Interaction contrasts will include polynomial trends across time, focusing on a linear trend suggesting improvement and a quadratic trend suggesting that improvement is leveling off. As part of our analysis, we will also include the interaction between treatment and ARDS severity in the model. Because the study is not powered for the interaction between treatment and severity of ARDS, this test will be exploratory. We will also perform post-hoc analyses within each severity group to generate hypotheses for future study.

10.4.3 ANALYSIS OF THE SECONDARY AND EXPLORATORY ENDPOINTS

LIS, PaO₂/FiO₂, oxygenation index (OI), dead space fraction (Vd/Vt), and SOFA will be analyzed using repeated measures analysis of covariance (ANCOVA) to assess the effects of treatment, time, and the interaction between time and treatment, while incorporating between-patient variation in baseline measurements and important covariates including severity of ARDS (SAS PROC MIXED). Interaction contrasts will include polynomial trends

across time, focusing on a linear trend suggesting improvement and a quadratic trend suggesting that improvement is leveling off. As part of our analysis, we will also include the interaction between treatment and ARDS severity in the model. Because the study is not powered for the interaction between treatment and severity of ARDS, this test will be exploratory. We will also perform post-hoc analyses within each severity group to generate hypotheses for future study. For analysis of secondary endpoints, we will compare biological outcomes between treatment arms using the Mann-Whitney U or t-test for numerical endpoints and either χ^2 or Fisher's exact test for categorical outcomes.

Based on our prior work^{3,169}, the SD of the log-IL-18 is approximately 0.7. With 16 subjects in the placebo arm and 16 in the iCO arm, we will have > 80% power ($\alpha = 0.05$) to detect a difference in IL-18 levels of 0.5 log which corresponds to a 1.65-fold difference in plasma IL-18.

Based on an interim analysis of Cohort 1 in our Phase I trial, we will also have >80% power to detect a difference in a number of LM and SPMs including PGD₂, PGE₂, PGF_{2 α} , TXB₂, RvD2, and Mar1. Briefly, for multivariate statistical analysis, partial least square discriminant analysis (PLS-DA) will be performed as we have done previously¹⁷⁰. As we are testing multiple secondary and exploratory endpoints, a conservative 1% α level (ie. $p < 0.01$) will be used to accept statistical significance.

Ventilator-free days (VFDs), hospital- and ICU-free days will each be analyzed separately using ANCOVA with treatment arm as the main effect, however we will only be powered to see large changes in these outcomes (**Table 5**). Mortality will be analyzed using Cox regression models for time-to-death with treatment arm as the main covariate, and with important covariates including age in the model. HR and 95% CI for CO relative to placebo will be reported, along with estimated proportion surviving at 28, 60, and 180 days.

We will assess correlations between biomarkers and clinical and lung physiology outcomes including LIS, SOFA, VFDs, as well as 28- and 60-day hospital mortality. We will use multivariable linear regression as the primary model with LIS as the primary outcome variable. Biomarker levels tend to exhibit right skewedness and large outliers, so data will likely require log transformation. Additional predictor variables (such as demographic variables and comorbidities) will be specified *a priori* and interactions between those variables and biomarkers will be included in the model with adjustment for age as an important biological variable.

To evaluate the predictive ability of biomarkers for binary outcomes, we will use two methods. We will use c-statistics obtained from a logistic regression model to evaluate the effect of biomarker measurements on increasing the area under the receiver operating characteristic (ROC) curves. In addition, we will test if including measured biomarkers to models including important covariates results in an improvement in the net reclassification index as we have done previously for mtDNA³.

For secondary and exploratory endpoints, subjects may also be analyzed according to number of study drug doses completed.

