9.1.1 STUDY SAMPLE COLLECTION

Sample collection will be done according to the **Time-Events Schedule** in **Section 1.3**.

COHb Levels: COHb levels will be measured using the IL GEM Premier Co-oximeter at specified time points on Days 1 through 3. See **Section 9.5.2**.

Plasma Samples: Blood (4 mL on days 1-3) will be collected pre-treatment in EDTA anti-coagulated tubes for plasma isolation and measurement of biomarkers of mitochondrial dysfunction, inflammasome activation, lipid mediators, and cytokines. Blood will be collected (4 mL on days 1-3) post-treatment (at 90 min and 3 hrs). Blood (4 mL) will also be collected for plasma isolation on Day 5. Plasma will be obtained and divided immediately after centrifugation into equal aliquots in specified tubes and frozen at -80°C .

RNA Samples: On days 1-3, blood (2.5 mL) will be collected in Paxgene tubes for RNA isolation. Blood will be collected in Paxgene tubes before and after (at 90 min and 3 hrs) study drug administration, and frozen at -80°C . Blood (2.5 mL) will also be collected in Paxgene tubes for RNA isolation on Day 5, and frozen at -80°C .

DNA Samples: Cell pellets will be obtained for future DNA isolation from the blood collected in EDTA tubes on days 1-3 and on day 5. Cell pellets will be isolated pre-treatment and post-treatment (at 90 min and 3 hrs) on days 1 through 3. On days 1 and 5, the 8 mL tube may be used to isolate cell pellets if unable to obtain an adequate pellet from the 4 mL tube on that day.

Primary Cell Isolation: An additional 8 mL of blood will be drawn for isolation of peripheral blood mononuclear cells (PBMCs) pre-treatment on day 1 and post-treatment on day 3.

Urine Sample Collection: Between 50-100 mL of urine will be collected in a sterile specimen container on days 1-3 and on Day 5. Cell pellets will be isolated pre-treatment and post-treatment (at 90 min and 3 hours) to obtain RNA and protein, as well as mtDNA.

Discarded Specimens: Discarded bronchoalveolar lavage (BAL) fluid and plasma will be obtained (when available) for levels of cytokines, mediators/biomarkers, and protein. Plasma and BAL fluid will be divided into equal aliquots in specified tubes and frozen at -80°C .

A total of approximately 88.5 mL of blood will be collected for research samples during the study from each study subject as follows:

Sample collection	Day 1	Day 2	Day 3	Day 5	Total Volume
ABG, lactate, and COHb analysis	2.5 mL	2.5 mL	2.5 mL		7.5 mL

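### The secondary biomarkers are compared between arms with no baseline covariate although a pre-dose Day 1 value is collected. This costs precision, by an amount that depends on an unstated correlation, and the stated IL-18 power of over 80% is really about 50%

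*Combined protocol and SAP*

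**What the plan says.** Section 10.4.3 gives one sentence on the treatment comparison for the biomarkers listed in section 4.5 (autophagy markers, IL-18, lipid mediators, mitochondrial quality-control markers, inflammatory cytokines): "we will compare biological outcomes between treatment arms using the Mann-Whitney U or t-test for numerical endpoints". It names no covariate and no time point, and does not say whether the outcome is a level or a change.

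A baseline value exists. Under section 9.1.1, blood on Days 1 to 3 "will be collected pre-treatment in EDTA anti-coagulated tubes for plasma isolation and measurement of biomarkers of mitochondrial dysfunction", and RNA and urine pellets are also taken before dosing. Later samples follow each dose and on Day 5.

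Elsewhere the plan uses baseline. Section 10.4.2 models log mtDNA "while incorporating between-patient variation in baseline measurements", and section 10.4.3 does the same for LIS, PaO2/FiO2, OI, Vd/Vt and SOFA.

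For IL-18, section 10.4.3 says that "the SD of the log-IL-18 is approximately 0.7". "With 16 subjects in the placebo arm and 16 in the iCO arm", it claims more than 80% power at alpha 0.05 "to detect a difference in IL-18 levels of 0.5 log which corresponds to a 1.65-fold difference in plasma IL-18". It then sets a 1% significance level for secondary and exploratory endpoints. On distributions it warns: "Biomarker levels tend to exhibit right skewedness and large outliers, so data will likely require log transformation".

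**The concern.** The third study hypothesis (mitochondrial dysfunction, inflammasome activation, resolution of inflammation) rests on these comparisons, each made with 16 patients per arm and judged at 1%. Between-patient spread in cytokines and similar markers is large, and part of it is usually already present before dosing. If baseline log-IL-18 also has SD 0.7 (an assumption), the standard error of a chance baseline difference between arms is 0.7 × √(2/16) = 0.247 log, about half of the 0.5-log effect sought. A test that ignores the Day 1 value leaves that variation in the error term. The intervals are then wider than they need be, at a sample size with little to spare. The plan gives no reason for treating these biomarkers differently from mtDNA, which is measured in the same patients.

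**Working it through.** **Inputs.** From section 10.4.3: SD 0.7 and difference 0.5 on the natural log scale (exp(0.5) = 1.65, so the stated fold difference agrees), 16 per arm, alpha 0.05 for the power claim and 0.01 for significance. Sidedness is not stated for IL-18; two-sided is used, as in Table 7. The baseline-to-follow-up correlation ρ is not given anywhere and is **assumed**, range 0.2 to 0.7.

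**1. The plan's own figure.** Standard error = 0.7 × √(2/16) = 0.2475. Noncentrality = 0.5 / 0.2475 = 2.020, with 30 df.
- Two-sided 0.05: power 49.8% (normal approximation 52.4%; simulated Mann-Whitney about 47%).
- Two-sided 0.01: 25.3% (normal 28.9%; Mann-Whitney about 24%).
- One-sided 0.05: 62.9% (normal 64.6%).
- 14 per arm, roughly the number left after the 10% loss in section 10.2: 44.4% and 21.0% (two-sided 0.05 and 0.01).

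The claim of more than 80% is not reproduced. These inputs need about 31 per arm for 80%; 32 per arm gives 80.3%.

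**2. ANCOVA on the log Day 1 value.** Residual SD = 0.7 × √(1 − ρ²), 29 df, 16 per arm, two-sided. Gains are in points over the unadjusted t-test, from unrounded values.

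| ρ (assumed) | Residual SD | Noncentrality | Power, alpha 0.05 (gain) | Power, alpha 0.01 (gain) |
|---|---|---|---|---|
| unadjusted | 0.700 | 2.020 | 49.8% | 25.3% |
| 0.2 | 0.686 | 2.062 | 51.3% (+1.5) | 26.4% (+1.1) |
| 0.3 | 0.668 | 2.118 | 53.5% (+3.7) | 28.2% (+2.9) |
| 0.4 | 0.642 | 2.204 | 56.8% (+7.0) | 31.0% (+5.7) |
| 0.5 | 0.606 | 2.333 | 61.6% (+11.8) | 35.4% (+10.1) |
| 0.6 | 0.560 | 2.525 | 68.5% (+18.7) | 42.3% (+17.0) |
| 0.7 | 0.500 | 2.829 | 78.1% (+28.2) | 53.6% (+28.4) |

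At ρ = 0 the formula loses about 0.1 point, for the lost degree of freedom. Power reaches 80% only at ρ of about 0.72 (alpha 0.05) or 0.84 (alpha 0.01).

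**3. Check on the formula.** It treats the covariate as balanced between arms. Simulated ANCOVA, in which baseline differs by chance, gives 52.4%, 60.4% and 76.3% at alpha 0.05 for ρ = 0.3, 0.5 and 0.7, and 27.4%, 33.9% and 51.6% at alpha 0.01. These are about 1 to 2 points below the table (for example 61.6 − 60.4 = 1.2). So the gain at ρ = 0.2 is close to nil, and the cost at ρ = 0 is nearer 1 point than 0.1.

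**4. If change scores were intended.** With equal variances the SD of change is 0.7 × √(2(1 − ρ)).
- ρ = 0.5: SD 0.700, power at alpha 0.01 is 25.3%; ANCOVA gives 35.4%, 10 points more.
- ρ = 0.7: SD 0.542, power 45.6%; ANCOVA gives 53.6%, 8 points more.
- ρ = 0.3: SD 0.828, power 16.8%, below even the comparison of levels (25.3%).

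**The case against.** Several points on the other side have force.

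- **The size of the gain is not a plan figure.** A reader might infer that about 10 points of power are lost at the plan's own IL-18 inputs. The documents do not support that. Those inputs include no correlation, and 10 points is the result for one assumed value (0.5) at one alpha.
- **The plan may not discard baseline.** Section 10.4.3 does not say level or change, and section 10.4.2 applies the Mann-Whitney test to changes in mtDNA. The IL-18 power sentence speaks of levels, but it describes power and not the analysis variable. This stands as an ambiguity. It does not remove the point, because ANCOVA gains over either reading when the correlation is moderate.
- **Validity.** A reader might also infer that chance baseline imbalance makes the unadjusted test misleading. Under 1:1 randomisation that imbalance is already counted in the test's error rate, so type I error is preserved.
- **Outliers.** The expected skew and outliers are a fair reason to offer a rank test. They support keeping it as a sensitivity analysis, alongside a log-scale model.
- **Other sources.** The general approach in section 10.4 refers to a Statistical Analysis Plan for detail. The text supplied has no further rule for biomarkers. The regressions in section 10.4.3 relate biomarkers to clinical outcomes and do not estimate a treatment effect.
- **The 12 earlier subjects.** Adding their samples (section 4.5) does not rescue the IL-18 claim: 20 to 22 per arm gives about 60% to 66% at alpha 0.05, and the sentence itself specifies 16 and 16.

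**Conclusion.** The point holds as a loss of precision on secondary endpoints, and is worth correcting. As written, the biomarker comparison has no baseline term although the value is collected and used for comparable endpoints. The gain from adjustment is conditional: about 1 to 28 points for an assumed correlation of 0.2 to 0.7, with a slight loss at zero. It assumes a roughly linear relation on the log scale, and each marker will have its own correlation.

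What needs no assumed correlation is that the IL-18 power is about 50% at alpha 0.05 and 25% at alpha 0.01 (two-sided), against a stated figure above 80%. Adjustment should not be presented as restoring 80%: at a correlation of 0.5 it reaches 62% and 35%.

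**What to change.** In section 10.4.3:

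1. Analyse each numerical biomarker on the log scale at a named time point (for example Day 5) by ANCOVA, with treatment and the log pre-dose Day 1 value as the only covariate. Report the geometric-mean ratio with its confidence interval.
2. Keep the Mann-Whitney test as a sensitivity analysis, because outliers are expected.
3. Do not substitute change scores.
4. Restate the IL-18 power before adjustment as about 50% at alpha 0.05 and 25% at alpha 0.01. Any figure after adjustment should state the correlation assumed.

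This takes a few sentences and no new samples. The model spends one degree of freedom on the covariate. It is deliberately smaller than the mtDNA model in section 10.4.2, which also carries time, treatment-by-time, age, ARDS severity and treatment-by-severity terms; the power figures here do not apply to that larger model. If a separate analysis plan already specifies baseline adjustment for the biomarkers, section 10.4.3 need only be aligned with it and the power statement corrected.
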